Q2W = Every 2 weeks, IV = Intravenous

Phase 2 Design:

The phase 1b portion has been completed and the phase 2 portion of the protocol is now open.. There was one DLT identified in the phase 1b portion of the trial with 6 patients treated at dose Level 1. Therefore, the recommended phase 2 dose (RP2D) was established as **Level 1 (30mg/kg magrolimab starting cycle 1)**. The phase 2 portion will be a two-arm, randomized, open-label design. This cohort will seek to determine whether Hu5F9-G4 (magrolimab) plus

mogamulizumab will have improved efficacy as compared to mogamulizumab alone. We will enroll 82 patients with relapsed or refractory mycosis fungoides (MF) / Sézary Syndrome (SS). Patients will be randomized 1:1 to either Hu5F9-G4 (magrolimab) plus mogamulizumab or mogamulizumab alone. Randomization will be stratified by 2 characteristics: 1) Disease type (MF vs SS) and 2) Stage (1B-2A vs 2B-IV). To encourage accrual and to better assess the added effect of Hu5F9-G4 (magrolimab), the trial will allow for one-way crossover from the mogamulizumab only arm to the combination arm. Crossover will be allowed for patients with progressive disease or stable disease lasting 6 months. While not typically a criterion for crossover in other cancers, prolonged stable disease has not been an acceptable outcome for this patient population due to the presence of symptoms associated with ongoing disease.

TABLE OF CONTENTS

SCHEMA	3
1. OBJECTIVES	9
1.1 Primary Objectives.....	9
1.2 Secondary Objectives.....	9
1.3 Exploratory Objectives	9
2. BACKGROUND	9
2.1 Study Diseases	9
2.2 CTEP IND Agent.....	11
2.3 Other Agent.....	15
2.4 Rationale	16
2.5 Correlative Studies Background	20
3. PATIENT SELECTION	24
3.1 Eligibility Criteria	24
3.2 Exclusion Criteria	26
3.3 Inclusion of Women and Minorities	28
4. REGISTRATION PROCEDURES	28
4.1 Investigator and Research Associate Registration with CTEP	28
4.2 Site Registration.....	29
4.3 Patient Registration.....	32
4.4 General Guidelines.....	34
5. BIOMARKER, CORRELATIVE, AND SPECIAL STUDIES	34
5.1 Summary Table for Specimen Collection.....	34
5.2 Specimen Procurement Kits and Scheduling.....	36
5.3 Specimen Tracking System Instructions.....	36
5.4 Specimen Collection	40
5.5 Shipping Specimens from Clinical Site to the EET Biobank	42
5.6 Biomarker Plan	45
5.7 Integrated Correlative Studies.....	51
5.8 Exploratory/Ancillary Correlative Studies	51
6. TREATMENT PLAN	55
6.1 Agent Administration.....	55

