1.2 Secondary Objectives

1.2.1 Phase 1

1.2.2 To observe and record anti-tumor activity. Although the clinical benefit of these drugs has not yet been established, the intent of offering this treatment is to provide a possible therapeutic benefit, and thus the patient will be carefully monitored for tumor response and symptom relief in addition to safety and tolerability.

1.2.3 Phase 2

1.2.3.1 To compare the efficacy of the combination of Hu5F9-G4 (magrolimab) and mogamulizumab versus mogamulizumab alone with respect to the following endpoints:

- Overall Response Rate (ORR); Overall Response Rate lasting at least 4 months (ORR4); Overall Response Rate lasting at least 12 months (ORR12)
- Duration of response (DOR)
- Progression-free survival (PFS)
- Time to next treatment (TTNT)

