6.5 Duration of Follow-Up

Patients will be followed for two years after their last treatment, until progression, or until the start of the next significant treatment, whichever occurs first. Patients removed from study for unacceptable adverse event(s) will be followed until resolution or stabilization of the adverse event.

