6.6 Cross-over

6.6.1 Eligibility for cross-over:

Subjects randomized to the mogamulizumab-only arm will be eligible to cross-over to the combination arm of Hu5F9-G4 (magrolimab) and mogamulizumab if they meet EITHER of the following criteria:

1. Have received at least 2 full treatment cycles of mogamulizumab and meet global criteria for progression of disease
2. Have received at least 6 full treatment cycles of mogamulizumab and meet global criteria for stable disease

Additionally, to be eligible for cross-over, subjects must meet BOTH of the following criteria:

1. Meet the eligibility criteria at the time of cross-over. The only exception to the eligibility criteria will be that subjects who have active large cell transformation (LCT) at the time of cross-over will be eligible for cross-over.
2. Subjects must also have a skin biopsy performed within 4 weeks prior to cross-over with a pathologic diagnosis confirming cutaneous lymphoma. It is strongly recommended to perform molecular studies of TCR clonality if there is ambiguity in the diagnosis. This criteria is to exclude the possibility of progression incorrectly being attributed to a mogamulizumab-associated rash.

Subjects will have 4 weeks from the date of progression to meet eligibility for cross-over.

6.6.2 Procedures related to cross-over:

Subjects who cross-over to the combination therapy arm will adhere to the study calendar. The following procedures do not need to be repeated at baseline if performed within 4 weeks of cross-over:

- Imaging
- Flow cytometry
- Skin biopsies
- Correlative blood collection

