9.4 Analysis of Secondary Endpoints

The analysis plan for the secondary objectives will be as follows:

Table 5: Analysis of Secondary Endpoints

Secondary Endpoint	Statistical Method
ORR, ORR4, ORR12	Chi-squared
PFS, DOR, TTNT	Kaplan-Meier method; Log- rank

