11. STUDY CALENDAR

Baseline evaluations are to be conducted within 1 week prior to start of protocol therapy. Scans and x-rays must be done \leq 4 weeks prior to the start of therapy. In the event that the patient's condition is deteriorating, laboratory evaluations should be repeated within 48 hours prior to initiation of the next cycle of therapy.

	Pre-Study	Priming	Cycle 1 ^m					Cycle 2 ^m					Cycle 3 ^m		Cycle 4-12 ⁿ		End of Treatment or Progression ^a
			Wk 1	Wk 1	Wk 2	Wk 3	Wk 4	Wk 1	Wk 2	Wk 3	Wk 4	Wk 1	Wk 3	Wk 1	Wk 3		
Hu5F9-G4 (magrolimab)		A	A	A	A	A	A	A	A	A	A	A	A	A	A		
Mogamulizumab			B	B	B	B	B		B			B	B	B	B		
Informed consent	X																
Demographics	X																
Medical history	X																
Concurrent meds ^b			X-----										X			X	
Physical exam	X	X	X	X	X	X	X	X	X	X	X	X	X	X		X	
Vital signs	X	X	X	X	X	X	X	X	X	X	X	X	X	X		X	
Height	X																
Weight	X	X	X				X					X		X			
Performance status ^c	X	X	X	X	X	X	X		X			X		X		X	
CBC w/diff, plt ^p	X	X ^p	X ^p	X	X	X	X	X	X	X	X	X	X	X			
Comprehensive Chemistry Panel ^d	X	X	X	X	X	X	X	X	X	X	X	X	X	X			
Pregnancy test ^e	X																
ABO/Rh type and screen, DAT ^f	X																
Antibody Screen ^g	X																
Extended RBC phenotyping including minor antigens such as CcDEe, Cw, MNSs, Kk, FyaFyb, and Jka Jkb ^{h,i}	X																
Adverse event evaluation			X-----										X			X	
mSWAT assessment/medical photography ^f		X						X					X	X ^f		X	
Imaging ^g	X												X ^g	X ^g		X ^g	
Flow Cytometry		X											X ^h	X ^h		X ^h	
FFPE biopsy tissue (optional)	X ^o																
Skin punch biopsies ^l	X			X								X				X	
Correlative blood collection ^k	X			X								X	X			X	

	Pre-Study	Prim ing	Cycle 1 ^m				Cycle 2 ^m				Cycle 3 ^m		Cycle 4-12 ⁿ		End of Treatment or Progression ^a
			Wk 1	Wk 1	Wk 2	Wk 3	Wk 4	Wk 1	Wk 2	Wk 3	Wk 4	Wk 1	Wk 3	Wk 1	Wk 3
A:	Hu5F9-G4 (magrolimab) : On Priming Week 1 only, a priming dose of 1 mg/kg Hu5F9-G4 (magrolimab) will be given. Then assigned dose on Cycle 1 Day 1, 8, 15, and 22, Cycle 2 Day 1, 8, 15 and 22, Cycle 3+ Day 1, 15. Cycles are 28 days long.														
B:	Mogamulizumab: 1mg/kg on Cycle 1 Day 1, 8, 15, and 22, Cycle 2+ Day 1, 15. Cycles are 28 days long.														
a:	Off-study evaluation. Cycle 12 (Week 48) visit may serve as end of treatment/progression visit														
b:	Starting from cycle 4, concurrent meds will be evaluated first week of every cycle														

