SD	Failure to attain CR, PR or PD representative of all disease	PR	No category has a PD and if any other category involved at baseline, no CR or PR in any		
		SD	CR/NI, PR, SD in any category and no category has a PD		
PD	Progressive disease	PD in any category			
Relapse	Recurrence disease in prior CR	Relapse in any category			

NI= noninvolved

12.1.4 Confirming early progression:

Immunotherapeutics may result in infiltration of immune cells leading to transient increase in the size in malignant lesions, or undetectable lesions becoming detectable. In cutaneous lymphoma this may manifest as worsening appearance of skin lesions or lymph nodes early in treatment. To allow sufficient time to differentiate such pseudoprogression from true progression, patients with early progression events may continue on treatment with increased surveillance until true progression is confirmed. Treatment beyond progression in such cases can occur at the investigator's discretion after approval by the Principal Investigator.

Skin progression: Patients with progression in the skin compartment documented any time up to, and including, their assessment at 12 weeks may continue on treatment if they meet all of the following criteria:

1. Progression cannot be due to development of new tumors (T3) disease in a patient with T1, T2, or T4 disease
2. Patients must have monthly mSWAT assessments while continuing treatment
3. During this period of unconfirmed progression, the mSWAT score on each subsequent assessment must be less than or equal to the most recent mSWAT score (i.e. the mSWAT must improve with each subsequent evaluation)

It is strongly encouraged that a skin biopsy be performed if the investigator suspects pseudoprogression in the skin. The patient may continue with monthly mSWAT examinations until Cycle 6. By Cycle 6, the patient must meet criteria for stable disease or better to continue on treatment. If progression is confirmed by an increase in mSWAT in a subsequent evaluation, then the date of progression for endpoint analysis will be the first date of progression, not the

NCI Protocol #: 10384
Version Date: September 5, 2023
date of the confirmation.

Lymph node: Patients with progression in the lymph node compartment documented on their first scheduled assessment at 12 weeks may continue on treatment if they meet the following criteria:

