12.2 Definitions of Study Endpoints

Overall Response Rate (ORR): ORR is defined as the proportion of patients who have a partial or complete response to therapy as defined by the global response score.

Duration of Response (DOR): DOR is defined as the duration of overall response is measured from the time measurement criteria are met for CR or PR (whichever is first recorded) until the first date that recurrence or PD is objectively documented.

Overall Response Rate 4 (ORR4): ORR4 is defined as the proportion of patients who have a partial or complete response to therapy AND a duration of response \geq 4 months.

Overall Response Rate 6 (ORR6): ORR6 is defined as the proportion of patients who have a partial or complete response to therapy AND a duration of response \geq 6 months.

Overall Response Rate 12 (ORR12): ORR12 is defined as the proportion of patients who have a partial or complete response to therapy AND a duration of response \geq 12 months.

Progression-Free Survival (PFS): PFS is defined as the duration of time from start of treatment to time of progression or death, whichever occurs first.

Time to next treatment (TTNT): TTNT is defined as the duration of time from the start of treatment on this protocol to time of the next anti-neoplastic therapy.

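### Follow-up stops at progression and crossover is unclassified, so the between-arm TTNT comparison lacks the dates and the rule it needs

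*Combined protocol and SAP*

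**What the plan says.** Section 6.5 has patients "followed for two years after their last treatment, until progression, or until the start of the next significant treatment, whichever occurs first". Section 12.2 defines the endpoint without reference to progression: "TTNT is defined as the duration of time from the start of treatment on this protocol to time of the next anti-neoplastic therapy". Section 1.2 lists TTNT among the phase 2 endpoints to be compared between arms, and Table 5 in Section 9.4 assigns it "Kaplan-Meier method; Log- rank". No censoring rule for TTNT appears.

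The last column of the study calendar (Section 11) is the end-of-treatment or progression visit, with the footnote "Off-study evaluation. Cycle 12 (Week 48) visit may serve as end of treatment/progression visit".

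On crossover, the Schema states that "the trial will allow for one-way crossover from the mogamulizumab only arm to the combination arm". Section 6.6.1 opens two routes: progression after at least 2 full cycles, or stable disease after at least 6. Section 6.6.2 adds: "Subjects who cross-over to the combination therapy arm will adhere to the study calendar". Neither Section 9.4 nor Section 12.2 says whether starting the combination at crossover is a TTNT event.

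Some later dates could be caught by chance. Section 12.1.4 says "patients with early progression events may continue on treatment with increased surveillance until true progression is confirmed". Section 6.3 and the calendar record concurrent medications up to the last visit. Section 6.5 follows patients removed for adverse events until these resolve or stabilize.

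**The concern.** A new anti-cancer therapy commonly follows progression, and progression ends protocol treatment (Section 6.4). A follow-up rule that stops at progression therefore stops just before many TTNT events. Log-rank and Kaplan-Meier assume that a censored patient has the same outlook as one still observed. A patient censored at progression is far more likely than others to start new therapy soon.

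The arms are also not alike. After progression, only control patients have a planned route to a recorded new regimen. Section 2.4.5 explains why new therapy matters in this disease, so a distorted TTNT result would be read with interest. Dates that were never collected cannot be recovered by analysis.

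The wording differs as well: Section 6.5 stops at the next treatment that is significant, while Section 12.2 counts the next anti-neoplastic therapy.

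**Working it through.** The plan states no event count, power or test level for TTNT, so there is no TTNT figure to reproduce. Its one efficacy power figure, 86% for ORR6 (Section 9.1), reproduces at 86.7% by normal approximation to the stratified test and plays no part below.

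**Step 1. Which TTNT dates does the plan collect?**

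| Course | Combination | Control |
|---|---|---|
| New therapy before progression | Recorded; it ends follow-up | Recorded; it ends follow-up |
| Progression, then off-protocol therapy | No stated collection | No stated collection |
| Progression, then crossover | Not available | Recorded; calendar restarts |
| Stable disease after 6 cycles, then crossover | Not available | Recorded; calendar restarts |

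**Step 2. Scale of the progression route.** Inputs: median PFS 7.7 months and 41 per arm (Section 9.1); 2 cycles = 8 weeks = 1.84 months; 12 cycles = 48 weeks = 11.04 months. Assumed: exponential times. Share of controls with a PFS event in weeks 8 to 48 = 0.5^(1.84/7.7) − 0.5^(11.04/7.7) = 0.847 − 0.370 = 0.477, and 0.477 × 41 = 19.6 patients. This is an upper figure for progression crossover, because PFS includes deaths.

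**Step 3. Share of events without a planned date.** Assume that switching before progression also has a constant hazard, with median m months. Progression then comes first with probability m/(m + 7.7):
- m = 12: 12/19.7 = 61%
- m = 18: 18/25.7 = 70%
- m = 36: 36/43.7 = 82%

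A simulation with a mean 2-month gap from progression to next therapy and follow-up capped at 35 months loses the same shares in the combination arm. The apparent median TTNT there is 12 months, 18 months and not reached, against 5.9–6.0, 6.8–6.9 and 8.1 months with complete dates. With no crossover the hazard ratio stays at 1.00 to 1.03: the curves are wrong, but equally so in both arms.

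**Step 4. Crossover counted, no true difference.** In the same simulation, if 30% of progressing controls cross over, the hazard ratio is 0.70, 0.60 and 0.44, against 0.98, 0.96 and 0.96 with complete dates. At 60% it is 0.54, 0.45 and 0.32, against 0.93, 0.92 and 0.93.

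A second simulation assumed a two-sided 5% log-rank test (2.5% in the direction of the combination), switching before progression in 10–40% of controls, and 25–75% uptake of progression crossover. The combination is falsely favoured in 9% to 86% of trials, or in 4% to 17% if half of the other progressors in both arms are caught incidentally. The width of that range shows how far the size rests on the assumptions.

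**Step 5. Stable-disease crossover.** Now suppose every later date is collected in both arms and crossover counts. Add stable-disease crossover at week 24. Treat 72% of patients still event-free as non-responders (1 − 0.28, from the 28% ORR in Section 2.3.1; probably too high, because responders are over-represented among them). The combination is still falsely favoured in about 8% of trials at 25% uptake and up to about 50% at 75%. These control-only events arise before progression, so collecting dates after progression cannot remove them.

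**Step 6. Crossover not counted.** Planned events then come mainly from switching before progression. If the combination halves the progression hazard but leaves switching unchanged, those events occur at the same rate in both arms by construction, and the test rejects in about 3% of trials. Keeping crossover uncounted and adding collection (50% uptake, switching unchanged) gives 5% to 38%. At 75% uptake, with switching and post-crossover hazards both halved, collection gives 11%, 14% and 24% against 10%, 17% and 32% without it (10%, 20% and 40% switching). Collection therefore helps only together with a settled crossover rule.

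**The case against.** Several counter-arguments carry weight.

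- **Calendar silence is weak evidence.** The calendar also omits the two-year follow-up that Section 6.5 requires for patients without progression. The case report forms are not in the documents, and Section 13.2.2 allows customized ones. This stands: the point is that no collection is stated, and it rests on Section 6.5 rather than on the calendar.
- **Informative censoring is not written in the plan.** This stands. It is an inference that holds if patients are censored when follow-up ends.
- **Some dates will be caught anyway.** This is true for treatment past early progression, adverse-event follow-up and concurrent medications at the last visit. Switching before progression, which Section 2.4.5 describes as frequent, is fully captured. None of this is planned collection of therapy after progression.
- **Progression crossover may not occur.** Section 6.6.1 requires the eligibility criteria to be met at crossover, with active large cell transformation as the only exception, while exclusion 3.2.2 bars prior progression on mogamulizumab. If Section 3.2 applies at crossover, that route closes. The stable-disease route would remain.
- **TTNT is one of six secondary endpoints, with no alpha, power or decision rule.** This limits the weight of the point but does not remove the defect.

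A reader might take the upper simulated error rates as a forecast. The documents give no switching rate, crossover uptake or TTNT test level, so they support no such forecast. A reader might also infer that collecting the dates by itself repairs the comparison; Step 5 shows that it does not.

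**Conclusion.** The point holds in a limited form. As written, the protocol stops observation at progression, states no later collection of subsequent therapy, and leaves both the TTNT censoring rule and the status of crossover open. If censoring occurs when follow-up ends, patients who progress before new therapy are informatively censored, apart from incidental capture.

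If crossover counts, the comparison is biased toward the combination. The part due to progression crossover is made worse by Section 6.5; the part due to stable-disease crossover is independent of it. If crossover does not count, the comparison rests mainly on switching before progression and largely misses benefit from delayed progression.

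The direction follows from the text. The size does not: it rests on assumed switching, uptake, incidental capture, test level and exponential times. A reader might infer that the trial's main conclusions are at risk. They are not: ORR6, the other response rates, PFS and DOR do not depend on therapy dates after progression and are untouched by this defect.

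**What to change.** - **Section 6.5.** Keep response follow-up as it is. In both arms, after progression, record the date and type of the first subsequent anti-neoplastic therapy and the date of death, by chart review or phone, up to the existing two-year limit.
- **Sections 12.2 and 9.4.** State how progression crossover, stable-disease crossover, death and end of follow-up are handled for TTNT. Add a sensitivity analysis under the other crossover classification. State that collection alone does not remove the effect of control-only crossover.
- **Wording.** Use one description of the next therapy in Sections 6.5 and 12.2.
- **Crossover eligibility.** Reconcile Section 6.6.1 with exclusion 3.2.2, because together they determine whether progression crossover occurs.
- **Fallback.** If dates after progression will not be collected, report TTNT descriptively only.

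The cost is a protocol amendment across the participating organizations, one case report form page and brief site checks after progression. No visits, scans or patients are added.

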6.6 Cross-over

6.6.1 Eligibility for cross-over:

Subjects randomized to the mogamulizumab-only arm will be eligible to cross-over to the combination arm of Hu5F9-G4 (magrolimab) and mogamulizumab if they meet EITHER of the following criteria:

1. Have received at least 2 full treatment cycles of mogamulizumab and meet global criteria for progression of disease
2. Have received at least 6 full treatment cycles of mogamulizumab and meet global criteria for stable disease

Additionally, to be eligible for cross-over, subjects must meet BOTH of the following criteria:

1. Meet the eligibility criteria at the time of cross-over. The only exception to the eligibility criteria will be that subjects who have active large cell transformation (LCT) at the time of cross-over will be eligible for cross-over.
2. Subjects must also have a skin biopsy performed within 4 weeks prior to cross-over with a pathologic diagnosis confirming cutaneous lymphoma. It is strongly recommended to perform molecular studies of TCR clonality if there is ambiguity in the diagnosis. This criteria is to exclude the possibility of progression incorrectly being attributed to a mogamulizumab-associated rash.

Subjects will have 4 weeks from the date of progression to meet eligibility for cross-over.

6.6.2 Procedures related to cross-over:

Subjects who cross-over to the combination therapy arm will adhere to the study calendar. The following procedures do not need to be repeated at baseline if performed within 4 weeks of cross-over:

- Imaging
- Flow cytometry
- Skin biopsies
- Correlative blood collection

7. DOSING DELAYS/DOSE MODIFICATIONS

Dose Level	Hu5F9-G4 (Magrolimab) Maintenance Dose	Mogamulizumab
-1	1 mg/kg IV priming dose; Then 20 mg/kg IV weekly in Cycles 1 & 2 followed by Q2W in \geq Cycle 3. Give before mogamulizumab.	Weekly for cycle 1, then Q2W starting from cycle 2
1	1 mg/kg IV priming dose; Then 30 mg/kg IV weekly in Cycles 1 & 2	Weekly for cycle 1, then Q2W starting from cycle 2

	followed by Q2W in \geq Cycle 3. Give before mogamulizumab.	
--	--	--

Dose reductions are not required for Hu5F9-G4 (magrolimab), except in case of anemia. For all other treatment-related adverse events, Hu5F9-G4 (magrolimab) can be reduced by 1 dose level if a Grade 3 or higher AE that is related to Hu5F9-G4 (magrolimab) is observed and does not resolve within 2 weeks.

The following modifications should be performed for treatment-related adverse events.

Nausea	Management/Next Dose for Hu5F9-G4 (magrolimab) and Mogamulizumab
\leq Grade 1	No change in dose
Grade 2	Hold until \leq Grade 1. Resume at same dose level.
Grade 3	Hold* until $<$ Grade 2. Resume at one dose level lower, if indicated.
Grade 4	Off protocol therapy
*Patients requiring a delay of >2 weeks should go off protocol therapy.	
Recommended management: antiemetics.	

Vomiting	Management/Next Dose for Hu5F9-G4 (magrolimab) and Mogamulizumab
\leq Grade 1	No change in dose
Grade 2	Hold until \leq Grade 1. Resume at same dose level.
Grade 3	Hold* until $<$ Grade 2. Resume at one dose level lower, if indicated.
Grade 4	Off protocol therapy
*Patients requiring a delay of >2 weeks should go off protocol therapy.	
Recommended management: antiemetics.	

Diarrhea	Management/Next Dose for Hu5F9-G4 (magrolimab) and Mogamulizumab
\leq Grade 1	No change in dose
Grade 2	Hold until \leq Grade 1. Resume at same dose level.
Grade 3	Hold* until $<$ Grade 2. Resume at one dose level lower, if indicated.
Grade 4	Off protocol therapy
*Patients requiring a delay of >2 weeks should go off protocol therapy.	
Recommended management: Loperamide antidiarrheal therapy Dosage schedule: 4 mg at first onset, followed by 2 mg with each loose motion until diarrhea-free for 12 hours (maximum dosage: 16 mg/24 hours) Adjunct anti-diarrheal therapy is permitted and should be recorded when used.	

Neutropenia	Management/Next Dose for Hu5F9-G4 (magrolimab) and Mogamulizumab
≤ Grade 1	No change in dose
Grade 2	Hold until ≤ Grade 1. Resume at same dose level.
Grade 3	Hold* until < Grade 2. Resume at one dose level lower, if indicated.
Grade 4	Off protocol therapy
*Patients requiring a delay of >2 weeks should go off protocol therapy.	
Recommended management: Growth factor	

Thrombocytopenia	Management/Next Dose for Hu5F9-G4 (magrolimab) and Mogamulizumab
≤ Grade 1	No change in dose
Grade 2	Hold until ≤ Grade 1. Resume at same dose level.
Grade 3	Hold* until < Grade 2. Resume at one dose level lower, if indicated.
Grade 4	Off protocol therapy
*Patients requiring a delay of >2 weeks should go off protocol therapy.	

Anemia	Management/Next Dose for Hu5F9-G4 (magrolimab)	Management/Next Dose for Mogamulizumab
≤ Grade 1	No change in dose	No change in dose
≤ Grade 2	No change in dose	No change in dose
Grade 3 hemolytic anemia that is medically significant (requiring hospitalization or prolongation of existing hospitalization, disabling, or limiting self-care ADLs)	First occurrence: Reduce by 1 dose level. 
 • If recurs after 1 dose level reduction: permanently discontinue unless patient is clinically benefitting. • Second occurrence: permanently discontinue 	Hold* until ≤ Grade 2. Resume at same dose level.
Grade 4	First occurrence: permanently discontinue unless patient is clinically benefitting.**	First occurrence: permanently discontinue unless patient is clinically benefitting.**
*Patients requiring a delay of >2 weeks should go off protocol therapy.		
**If Grade 4 anemia is unrelated to underlying disease, permanently discontinue Hu5F9-G4 (magrolimab) regardless of clinical benefit. Mogamulizumab may be resumed if anemia is resolved to Grade ≤ 2 and if there may be a clinical benefit from the treatment.		
Recommended management: Transfusions as per section 7.1		

Rash* (including maculopapular, pruritus, erythroderma, photosensitivity, and skin pain)	Management/Next Dose for Hu5F9-G4 (magrolimab)	Management/Next Dose for Mogamulizumab
Grade 2	Magrolimab ** should be continued without dose modification.	Mogamulizumab *** may be held at investigator's discretion.
Grade 3	Magrolimab ** may be held at the investigator's discretion.	Mogamulizumab *** may be held at investigator's discretion.
Grade 4	Off protocol therapy	Off protocol therapy

*It is recommended to perform skin biopsies when possible with molecular T-cell receptor clonality studies to help distinguish rash from progressive disease
 
** Magrolimab may be held at the investigator's discretion for up to 2 weeks from the time of the scheduled infusion for grade 3 rash. Patients requiring a magrolimab delay of >2 weeks from their scheduled infusion should go off protocol therapy. Upon restarting magrolimab after a delay, there will be no dose reduction.
 
*** Mogamulizumab may be held up to 4 weeks from the time of the scheduled infusion for grade 2-3 rash. Patients requiring a mogamulizumab delay of >4 weeks from their scheduled infusion should go off protocol therapy. Upon restarting mogamulizumab after a delay, there will be no dose reduction.
		

Recommended management: High potency topical steroids may be used for grade 2-3. Subjects should apply topical steroids only to areas of suspected rash and avoid areas of known lymphoma disease and should try to reduce topical steroids to medium or low potency as tolerated. For grade 2, systemic corticosteroids may be given. For grade 3, systemic corticosteroids should be given. A dose of 40mg prednisone daily or equivalent is suggested. If systemic corticosteroids are given, efforts should be made to taper as tolerated to a dose of 10mg prednisone daily or equivalent.
		

All Other Drug-related Toxicity***	Management/Next Dose for Hu5F9-G4 (magrolimab) and Mogamulizumab
Grade 3	Hold ** until \leq Grade 2.
Grade 4	Off protocol therapy

* Patients with intolerable or persistent Grade 2 drug-related AE may hold study medications for up to 2 weeks at physician discretion.
 
**Patients requiring a delay of >2 weeks should go off protocol therapy.
 
*** Lymphopenia and/or leukopenia are the pharmacologic effect of mogamulizumab and will not be considered an AE for this study. However, neutropenia will be considered an AE and managed as above.
	

All Other Drug-related Toxicity***	Management/Next Dose for Hu5F9-G4 (magrolimab) and Mogamulizumab
---	---

Dosing interruptions are permitted in the case of medical/surgical events or logistical reasons not related to study therapy (e.g., elective surgery, unrelated medical events, patient vacation, and/or holidays). Patients should be placed back on study therapy within 2 weeks of the interruption. The reason for interruption should be documented in the patient's study record.

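### For a clinically benefitting patient with a second medically significant Grade 3 hemolytic anemia, the Section 7 Anemia table both permits and forbids further magrolimab

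*Combined protocol and SAP*

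**What the plan says.** The Anemia table in Section 7 has separate columns for magrolimab and mogamulizumab. The row at issue covers "Grade 3 hemolytic anemia that is medically significant (requiring hospitalization or prolongation of existing hospitalization, disabling, or limiting self-care ADLs". Its magrolimab cell holds three lines:

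- "First occurrence: Reduce by 1 dose level"
- "If recurs after 1 dose level reduction: permanently discontinue unless patient is clinically benefitting"
- "Second occurrence: permanently discontinue"

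The mogamulizumab cell in the same row gives a single instruction (hold until the event improves, then resume at the same dose level).

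The text before the tables gives the general rule: "Dose reductions are not required for Hu5F9-G4 (magrolimab), except in case of anemia". It does not mention recurrence. The dose-level table at the start of Section 7 lists two levels only, Level 1 and Level -1. Section 6.1 fixes Level 1 as the recommended phase 2 dose.

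**The concern.** A dose-modification table should give a site one action for each event. Here two adjacent lines appear to describe the same event, and only one of them carries an exception for clinical benefit. If so, two sites could follow the protocol to the letter and treat the same patient in opposite ways, and monitoring would have no basis for calling either action a deviation.

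The protocol itself treats this event as serious. Section 6.2 exempts ordinary Grade 3 anemia from the dose-limiting toxicity definition but keeps Grade 3 hemolytic anemia as dose-limiting. The trial is multicentre, with ten participating organizations listed. Patients who cross over follow the combination schedule (Section 6.1), so the same row would apply to them.

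**Working it through.** No figure in the plan bears on this point, so there is nothing to recalculate. The check has three steps: decide which event each line addresses, list the cases, and look for a rule elsewhere that settles any conflict.

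**Step 1: which event each line addresses.** The first line attaches no condition to the reduction. A patient managed under this row has therefore been reduced by one level before any second event. The second line addresses a recurrence after one reduction, and the third addresses the second occurrence. For such a patient these are the same event.

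**Step 2: the cases.**

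| Event | Clinically benefitting? | Line on recurrence after reduction | Line on second occurrence | Result |
|---|---|---|---|---|
| First | Either | Not applicable | Not applicable | One instruction: reduce by one level |
| Second | No | Stop permanently | Stop permanently | The lines agree |
| Second | Yes | Exception applies; may continue | Stop permanently | The lines conflict |

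One case of three is contradictory, and it is the case for which the exception was written. The dose ladder offers no middle course. From Level 1, one reduction leads to Level -1, and no lower level is listed. What remains is to continue or to stop, which is what the two lines disagree about.

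**Step 3: a rule elsewhere.**

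- The single-asterisk footnote to the Anemia table concerns delays of more than two weeks.
- The double-asterisk footnote concerns Grade 4 anemia and is not attached to the Grade 3 row.
- The general text before the tables is silent on recurrence.
- Section 7.1.4 deals with hemoglobin checks, cross-matching and transfusion.
- Section 6.4 lists unacceptable adverse events and investigator judgment among the reasons to end treatment, but does not say which line governs.

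None of these settles the conflict.

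**The case against.** The best defence is a sequential reading: reduce at the first event; at a recurrence, stop unless the patient is benefitting; at a second recurrence, which would be a third event, stop in every case. The layout gives this some support, since the last two lines are set as bullets after the first, and list nesting may have been lost when the document was read from PDF. What stands of it is that the authors may have meant this. But the text does not say so, and the paired labels of first and second occurrence count events from one. If a third event was intended, the wording still fails to convey it and needs the same correction.

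A second defence is that Section 6.4 lets treatment end for unacceptable toxicity or on the investigator's judgment, so the benefit exception never compels further dosing. That is correct, and for that reason uneven risk to patients is not demonstrated here. It does not tell a site whether continuing is allowed.

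A reader might infer three stronger points. The documents do not support them.

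- **That the Grade 4 row contradicts itself as well.** Its exception for clinical benefit carries a marker to a footnote that limits it: "If Grade 4 anemia is unrelated to underlying disease, permanently discontinue Hu5F9-G4 (magrolimab) regardless of clinical benefit". For magrolimab that is a rule, an exception and a stated limit on the exception, and a site that follows the marker reaches one answer.
- **That the conflict distorts the toxicity review trigger in Section 9.1.** That trigger needs at least 2 patients, and more than 30%, to stop the doublet for adverse events before the third cycle. To be counted differently because of these lines, a patient would need two medically significant hemolytic episodes, a reduction between them and clinical benefit at the second. All of this would have to fall within the priming week and two 28-day cycles, or 7 + 2 × 28 = 63 days (9 weeks). The 12-week re-evaluation in Section 12 falls after that. The documents give no reason to expect such patients in any number.
- **That the anemia frequencies in Section 2.2.1.2.2 measure the problem.** Those figures cover all treatment-related anemia and all related serious anemia reactions. The conflict concerns only a recurrence of medically significant Grade 3 hemolytic anemia, for which no rate is given.

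**Conclusion.** The point holds, within a narrow scope. As written, the magrolimab cell gives conflicting instructions for a second medically significant Grade 3 hemolytic anemia in a patient who is clinically benefitting, and no other part of the protocol resolves it. For patients who are not benefitting the lines agree, and the mogamulizumab instruction is unaffected.

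The conclusion rests on two assumptions. The reduction is made as the first line directs before the second event, and the occurrence labels count events in the ordinary way. The number of patients affected is not given and may be small. No effect on power, type I error or the primary analysis is claimed. The consequence is operational: handling may differ between sites, and deviations in this situation cannot be judged. It merits correction because the protocol treats the event as dose-limiting and the correction costs very little.

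**What to change.** The sponsor's clinical team should reconcile the two lines so that a second medically significant Grade 3 hemolytic anemia has one instruction, whether or not the patient is benefitting. If the lines were meant for different events, the table should say which event each one covers. Which rule applies is a clinical decision for that team, and this review does not suggest one. The change is a table edit in the next amendment, with no effect on sample size, data collection or the analysis plan.
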